1. INTRODUCTION

In Malawi, adult HIV prevalence remains high, with pronounced social and economic inequity in HIV testing and linkage to HIV services. Self-testing for HIV (HIVST) is becoming an established option for providing highly accurate results when used by lay individuals. However, more research is needed to establish the potential role of HIVST in rural Africa, where coverage of HIV testing services is especially low. This project aims to investigate the feasibility, affordability, and health and social impact of introducing HIVST to rural communities through existing community-based distribution agents (CBDA).

The HIV STAR Malawi General Population study includes a cluster-randomized trial investigating the effects of introducing HIVST through CBDAs in 4 districts in Malawi's Southern region. This research protocol is nested within the UNITAID/Population Services International (PSI) HIV Self-Testing Africa (STAR) project. PSI is leading the implementation of this project, with the evaluation conducted by the Malawi-Liverpool-Wellcome Trust (MLW) and the London School of Hygiene and Tropical Medicine (LSHTM).

This document outlines the plan for primary analysis of the STAR Malawi cluster randomized trial for the publication of primary results. Only the randomization of clinics to the HIVST intervention is discussed below; the planned second randomization of CBDAs to home-based ART initiation was not implemented due to delays in study initiation.

2. TRIAL DESIGN

2.1 Research objectives

The primary objectives of this trial are to: estimate the impact of introducing HIVST through CBDAs on i) coverage of recent testing (within the last 12 months) and lifetime testing among residents ages 16 years and older and ii) cumulative incidence of ART initiation per 100,000 population in primary care clinics.

2.2 Trial arms, randomization, and blinding

This study will be conducted in rural settings in Malawi's Southern region. The study was originally designed with two randomization stages, but only one was completed. We refer to outcomes for the first randomization only.

Stage 1 randomization. The first randomization was conducted at the clinic (cluster) level, because the intervention is administered at this level. Primary care clinics offering ART services (22 total) and their catchment areas were randomized to either HIVST or standard of care (SOC) arms.

- **Arm A (11 clinics). HIVST.** All CBDAs working within the catchment area of clinics in the HIVST arm were trained by PSI to provide HIVST (OraQuick HIV Self-Test). Some CBDAs had been working with PSI before the study to distribute reproductive health products, while others were hired and trained for the study. CBDAs provide i) brief pre-test information; ii) a self-referral form with all kits to facilitate linkage into HIV care and prevention services; iii) generic or results-based post-test advice, depending on disclosure of results to CBDAs.
- **Arm B (11 clinics). SOC.** In the SOC arm, no kits will be provided to CBDAs working with PSI, and no additional CBDAs were trained to distribute reproductive health products.

Allocation was completed using restricted randomization, with allocation options restricted to ensure balance by geography; proportion of positive tests in each clinic; total number of tests

conducted in each clinic; and catchment population. To ensure that intervention and control clinics were distributed geographically across the study area, we applied the following restrictions.

- (1) **Blantyre district:** 8 clinics were located in Blantyre. Of these, at least 3 and no more than 5 were assigned to the intervention. 4 clinics (Madziabango Health Centre, Mpemba Health Centre, Pensulo Health Centre, and Soche Maternity) were located south of Blantyre. Of these, at least 1 and no more than 3 were assigned to the intervention. 4 clinics (Chikowa Health Centre, Dziwe Health Centre, Lirangwe Health Centre, and Makata Heath Centre) were located north of Blantyre. Of these, at least 1 and no more than 3 were assigned to the intervention.
- (2) **Machinga district:** 7 clinics were located in Machinga. Of these, at least 3 and no more than 4 were assigned to the intervention.

2.3 Duration of intervention and timing of baseline and endline surveys

The HIVST intervention will be evaluated after at least 12 months of implementation. The interventions will be implemented across all areas in September 2016.

The baseline household survey was conducted between May-August 2016, and the household endline survey is expected to begin in September 2017 and end in December 2017-January 2018. Clusters will be surveyed in the same order for the baseline and endline surveys.

2.2 Study population and informed consent

Selection of clinics and evaluation areas. The population included in the impact evaluation are all residents ages 16 and older living in selected evaluation villages and areas located in 4 districts.

22 clinics were selected from rural areas within these districts for inclusion in the study. We identified clinics in areas where PSI had existing CBDAs of reproductive health services and that offered ART initiation. 23 clinics met these criteria, and the clinic with the lowest HIV prevalence was removed.

While HIVST distribution will occur across the entire catchment area of randomly selected clinics, evaluation data collection, including both household survey data collection and clinic data extraction, will be conducted only within selected areas. Evaluation villages represent villages selected for inclusion in the household survey. Evaluation areas represent the area of residence for clients whose data will be captured at the clinic.

Two villages in each cluster served as evaluation villages, with one village randomly receiving the baseline survey and the other receiving the endline survey. Eligibility requirement for the evaluation villages include:

- Location within the catchment area of an eligible ART clinic, with the clinic acting as the most dominant source of ARTs for the village.
- Presence of at least one active PSI CBDA.
- Population of at least 250 residents (ages 16 years and older) per village.
- Road access for most/all of the year.
- Sufficient distance and separation from administrative boundaries and other intended evaluation villages to minimise 1) 'contamination' between HIVST and control villages, and 2) missed linkage to events from seeking HIV care at a remote clinic not included in the evaluation.
- Villages delineated by natural boundaries (e.g., rivers, roads, forests, etc.) will be preferentially selected.

Selection of respondents for baseline and endline surveys. Within evaluation villages, all households were enumerated and a variable fraction were selected to ensure that at least 250 residents (16 years and older) within households were surveyed. Within selected households, all eligible household members were interviewed with the basic questionnaire, and 20% of surveyed individuals received an extended questionnaire. All residents (ages 16 years and older) living in households within the intervention area are eligible to receive HIVST from CBDAs.

Participants provided verbal consent to participate in the baseline and endline surveys. Written informed consent (for residents ages 18 years and older) or assent with parental consent (for residents ages 16-17 years) was required to participate in the extended household survey and midline survey. Children ages 15 years and younger and those unable or unwilling to provide informed consent were excluded from the extended household survey.

3. OUTCOME EVALUATION AND DATA DESCRIPTION

3.1. PRIMARY OUTCOME AND SAMPLE SIZE CALCULATION

The primary outcome is the proportion of residents (16 years and older) who tested for HIV within the 12 months prior to the endline survey, which will begin at least 12 months after initiation of the HIVST intervention.

Outcome data (numerators and denominators) will be collected during the endline survey.

The survey sample size was estimated to ensure sufficient power to identify a difference in the primary outcome between those receiving the HIVST intervention and those receiving the SOC, and accounted for clustering by incorporating the cluster coefficient of variation (k) using methods outlined in Hayes and Moulton (2009). The average cluster size was estimated to be 250-500 residents (16 years and older), which is the average size of a rural village based on from previous experience in Malawi. We estimated that the cluster coefficient of variation (k) was 0.25. Using 2010 DHS data, the proportion of individuals testing in the last 12 months is estimated to be 25% to 40% and ever tested at 42% to 60% in the SOC arm. Using these assumptions, we have 80% power to detect a 30% relative difference in recent HIV testing and a 45% relative difference in lifetime HIV testing in the HIVST arm with $\alpha=0.05$.

3.2. SECONDARY OUTCOME

There are two secondary outcomes for the HIVST intervention. First, we will compare between arms the proportion of residents (16 years and older) who tested for HIV in their lifetime. Outcome data (numerators and denominators) will be collected during the endline survey.

We will also compare between arms cumulative incidence of ART initiation per 100,000 population for residents (16 years and older) during the intervention period, with ART clinic records used for this assessment. Data to measure ART initiation will be extracted from clinic records at three-month intervals for clients initiating ART from evaluation areas. The denominator will be the population (16 years and older) of evaluation areas, with data collected from village heads. We will cross-reference the population from village heads and baseline survey enumeration and ensure that differences between the two data sources are similar in the HIVST and SOC arm.

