4.5. ADJUSTED ANALYSIS

Factors for adjustment will be determined as stated above. If there are substantial baseline differences in recent testing across arms, we will adjust for baseline differences using cluster-level

summaries of baseline values. To adjust for other imbalances across arms, we will use endline measurements of these factors for adjustment, and will assume that there will be no substantial changes in these in the months between the baseline and endline surveys. The adjusted analysis will be the primary analysis.

The following covariates will be assessed as potential adjustors:

- Age
- Sex
- Marital status
- Educational attainment
- Assets index (in tertiles)

Logistic regression will be used to adjust for confounding bias at the individual level, adopting a two-stage approach as outlined in Hayes and Moulton (2009). In the adjusted analysis, the regression model will include terms for the individual-level adjustment factors, but not study arm. The fitted model will be used to obtain the difference and ratio of observed and expected events for each cluster. The ratio will be log-transformed as appropriate. A t-test will be used to estimate the risk difference and risk ratio and their respective 95% CIs and p-values. If adjustment for cluster level factors is considered necessary, this will be conducted at the second stage using linear regression, with appropriate adjustment for the degrees of freedom.

Because restricted randomization was used to allocate clinics, we will also report p-value and 95% confidence interval from a permutation test incorporating the restriction parameters described above (Li et al., 2016).

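### The individual-level first stage of the primary adjusted analysis cannot be fitted to ART initiation, and no adjusted cluster-level analysis is assigned to that outcome

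*SAP*

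**What the plan says.** Section 2.1 places ART initiation among the primary objectives, as "cumulative incidence of ART initiation per 100,000 population in primary care clinics". Section 3.2 lists it as a secondary outcome and defines it as "cumulative incidence of ART initiation per 100,000 population for residents (16 years and older) during the intervention period, with ART clinic records used". The numerator is "extracted from clinic records at three-month intervals for clients initiating ART from evaluation areas". For the population at risk, "The denominator will be the population (16 years and older) of evaluation areas, with data collected from village heads".

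Section 4.5 states: "The adjusted analysis will be the primary analysis". No outcome is named or excluded. The method follows: "Logistic regression will be used to adjust for confounding bias at the individual level, adopting a two-stage approach", and "the regression model will include terms for the individual-level adjustment factors, but not study arm". Observed and expected events per cluster are then compared by t-test. Apart from baseline recent testing, which enters as a cluster summary, the adjustors are endline measurements. Cluster-level factors may be added by linear regression at the second stage if this is thought necessary. A permutation test that respects the randomisation restrictions is also to be reported.

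Section 4.3 bars HIV status and self-reported ART use from the factors that can trigger adjustment. Section 4.4 gives the unadjusted analysis: a t-test on cluster risks or log risks with 20 degrees of freedom.

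**The concern.** The first stage needs a covariate record for every person in the denominator, whether or not that person had the event. The household survey supplies this for the two testing outcomes. For ART initiation the denominator is a headcount, so there is nothing to regress on and no covariate-adjusted expected count can be formed.

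ART initiation is the only one of the three outcomes that does not come from the household survey. As written, it has either a primary analysis that cannot be adjusted as described, or an adjusted analysis to be devised later. Measures of local HIV burden, which are plausibly related to how many people start ART, have no assigned place in the model for this outcome.

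**Working it through.** **1. What the first stage needs and what the SAP supplies for ART initiation**

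| Needed | Survey outcomes | ART initiation |
|---|---|---|
| Event status per person | Endline survey | Clinic records, initiators only |
| Covariates for people with the event | Endline survey | Not stated |
| Covariates for people without the event | Endline survey | None; the denominator is a population total |

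The survey cannot fill the gap as the plan stands. The section on study population distinguishes evaluation villages, where the survey is done, from evaluation areas, which define whose clinic data are captured. Only one village per cluster receives the endline survey. Section 3.2 uses the baseline enumeration only to cross-check population size. Even if clinic records held age and sex for initiators, the denominator would still lack them.

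**2. What is left when the first stage has no covariates**

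Let d_j be the events and N_j the headcount in cluster j, and let p = Σd_j / ΣN_j. An intercept-only first stage gives E_j = N_j × p. Then

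- log(d_j / E_j) = log(d_j / N_j) − log p
- (d_j − E_j) / N_j = d_j / N_j − p

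The term in p is the same in every cluster and cancels between arms. The adjusted ratio and difference are therefore the unadjusted ones of Section 4.4. A run on hypothetical data (22 clusters, headcounts of 1,500 to 5,000, risks of 0.006 and 0.005) gave a risk ratio of 1.0203 by both routes.

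**3. What one cluster-level covariate could gain**

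The SAP gives no ART rate, event count or between-clinic variance, so there is no figure of its own to reproduce. With 22 clusters and two arms the degrees of freedom are 22 − 2 = 20; one covariate leaves 19. If r is the within-arm correlation between the covariate and the cluster log rate, and the covariate is roughly balanced between arms, then

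CI width ratio = √(1 − r²) × t(19) / t(20) = √(1 − r²) × 2.0930 / 2.0860

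| r (assumed) | √(1 − r²) | Width ratio | CI narrower by |
|---|---|---|---|
| 0.3 | 0.954 | 0.957 | about 4% |
| 0.5 | 0.866 | 0.869 | about 13% |
| 0.7 | 0.714 | 0.717 | about 28% |

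At r = 0 the interval would be 2.0930 / 2.0860 = 1.003 times as wide, a loss of about 0.3%.

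**4. Whether a covariate is at hand**

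Section 2.2 on randomisation restricts on number of testers, proportion of tests positive and catchment population for each clinic. Proportion positive can be used directly. Positive tests per head of catchment follows as tests × proportion positive / catchment population. Neither needs new data.

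**The case against.** Section 4.5 can be read as written for survey outcomes. The sentence naming the primary analysis closes a paragraph about recent testing and endline measurements, and every covariate then listed is a survey variable. The SAP nowhere says that the adjusted analysis is primary for all outcomes; that is an inference from an unqualified sentence. This stands. But Sections 4.6 and 4.7 name the primary outcome when they mean it and Section 4.5 does not. On the narrow reading, ART initiation has no designated primary analysis, so a statement is needed either way.

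A reader might also infer that ART initiation has no executable or valid analysis. The document does not support that. The t-test of Section 4.4 runs on counts and headcounts, has a rule for clusters with no events, and is a valid randomised comparison. Adjustment is conditional on baseline imbalance, so with none found the two analyses coincide anyway.

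Nor is clinic HIV burden ignored. It entered the restricted randomisation, and the permutation test incorporates those restrictions. What is missing is its use to reduce residual variance in the model.

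The second-stage regression is a real route to adjustment, but a discretionary one. The only cluster-level adjustor that Section 4.5 names is baseline recent testing, and nothing ties the route to ART initiation.

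Finally, the choice of covariate is partly preference. Naming the unadjusted t-test as primary for ART initiation would also close the gap in specification, though without any gain in precision.

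**Conclusion.** The point holds as a gap in specification and efficiency, not as a flaw in validity. The logistic first stage of Section 4.5 cannot be fitted to ART initiation with the data the SAP describes, and without covariates it returns the unadjusted result of Section 4.4. No adjusted alternative is assigned to this outcome. The primary outcome, recent testing, is unaffected.

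The structural conclusion rests on the SAP's own definitions. The size of the gain does not: the correlations of 0.3 to 0.7 are assumed, and the resulting 4% to 28% is a range of possibilities rather than an estimate. The low end may be nearer the truth, because the clinic figures cover whole catchments while ART initiation is counted only in evaluation areas. That between-clinic variation in ART initiation is related to local HIV burden is plausible but not documented.

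**What to change.** - In Section 4.5, state that the individual-level logistic first stage applies to the two survey outcomes, recent and lifetime testing.
- For ART initiation, pre-specify as primary a linear regression of log cumulative incidence on arm plus one pre-trial clinic covariate, with clusters weighted equally, on 19 degrees of freedom. Keep the rule in Section 4.4 for clusters with no events.
- Name the covariate before arm labels are revealed, and include it whether or not the arms look imbalanced. Positive tests per head of catchment population, or proportion of tests positive, would serve. Give its source period and say whether tests or testers are counted.
- Report the unadjusted t-test (20 degrees of freedom) and the restricted permutation test alongside.

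The cost is SAP wording and one degree of freedom. No new data are needed, since the clinic figures were used for the randomisation. If the covariate proves unrelated to ART initiation, the interval widens by about 0.3%.

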3.3. ADDITIONAL ITEMS IN BASELINE AND ENDLINE SURVEY

In addition to the primary and pre-specified testing outcomes, the following data were collected from all respondents in the baseline and endline survey.

- **Questions on HIV testing and self-testing**, including partner testing and acceptability of HIVST.
- **Socioeconomic status and educational attainment** at household and individual level. Socioeconomic status was ascertained at the household level using an assets index and the household food insecurity assessment scale (HFIAS). All individuals were asked about salaried employment status and educational attainment.
- **Sexual behaviour**
- **Circumcision status and intention to access VMMC** (men only)

The extended survey was given to a 20% sub-sample of respondents, chosen at random using a random number generated in the electronic data capture tool. The extended survey included all elements from the baseline survey, as well as:

- **Detailed questions on previous three HIV tests**, including mode of testing, harms or regrets experienced after testing
- **Household decision-making** questions from Malawi Demographic and Health Survey 2010 (National Statistical Office (NSO) and ICF Macro, 2011, Bossuyt et al., 2015)
- **Conformity of masculine norms inventory** (Mahalik et al., 2003)
- **HIV care** (HIV-positive respondents only)
- **Stigma**, including anticipated stigma and knowledge of treatment effectiveness

- **Intimate Partner Violence** questions adapted from a measure used in the WHO Multi-Country Study on Women's Health and Domestic Violence (women only) (Garcia-Moreno et al., 2006)
- **Discrete choice experiments and costs of HIV testing**

4. STATISTICAL METHODS

All analyses will be completed in Stata version 14, on an intention-to-treat basis, and will use methods appropriate for cluster randomized trials with a small number of clusters. Reporting will conform to the 2010 Consort statement (Campbell et al., 2012).

4.1. RECRUITMENT AND REPRESENTATIVENESS OF SAMPLE

The trial flow chart will show the process of recruitment of study participants.

4.2. BASELINE AND ENDLINE SURVEY RESPONSE RATES

Baseline and endline survey response rates at the household and individual level will be calculated by cluster for the total population, as well as separately for women and men and adolescents ages 16-17 years and adults 18 years and older.

4.3. BASELINE COMPARABILITY OF ARMS (STAGE 1 RANDOMIZATION - HIVST INTERVENTION)

Following baseline data collection, we will summarize baseline data by arm by the following characteristics:

- Age
- Sex
- Marital status
- Educational attainment and socioeconomic status measured using assets variables.
- HIV status, previous HIV testing and self-reported ART use

Baseline analyses will be completed before the endline data collection period begins. The study team will identify substantial differences between arms in terms of the above factors (excluding HIV status and self-reported ART use) and adjust for endline measures of these baseline differences in the outcome analysis (see below). This assessment will not be completed using statistical tests, and p-values will not be shown, as any difference will be due to chance if the randomisation was correctly performed.

4.4. UNADJUSTED ANALYSIS

This analysis will give each cluster equal weight. The overall risk for each cluster will be calculated, and a log transformation will be applied to the summary value for each cluster if necessary. For binary outcomes where there are clusters with no events, one event will be added to all clusters so that the log transformation can be conducted. The mean of these log risks will be used to obtain the geometric mean (GM).

The risk difference, 95% CI and p-value will be estimated using a t-test of the risk by arm, based on 20 degrees of freedom. The risk ratio, 95% CI and p-value will similarly be estimated using a t-test of the log risk.

